8.3.2 Direct access to source data and documents

The sponsor will monitor the conduct of the trial by regular on-site monitoring visits and in-house data quality review. The frequency of on-site monitoring will be determined by assessing all characteristics of the trial, including its nature, objective, methodology and the degree of any deviations of the intervention from normal clinical practice.

The Investigator /institution will allow on-site trial-related monitoring, audits, IRB / IEC review and regulatory inspections. Direct access must be provided to the CRF and all source documents/data, including progress notes, copies of laboratory and medical test results, which must be available at all times for review by the CRA, auditor and regulatory inspector (e.g. FDA). The CRA and auditor may review all CRFs and informed consents. The accuracy of the data will be verified by direct comparison with the source documents described in [Section 8.3.1](#). The sponsor will also monitor compliance with the protocol and ICH GCP.

8.3.3 Storage period of records

Trial site(s):

The trial site(s) must retain the source and essential documents (including ISF) according to the national or local requirements (whatever is longer) valid at the time of the end of the trial.

Sponsor:

The sponsor must retain the essential documents according to the sponsor's SOPs.

8.4 EXPEDITED REPORTING OF ADVERSE EVENTS

BI is responsible to fulfil their legal regulatory reporting obligation and in accordance with the requirements. Any exemptions from expedited reporting are described under [Section 5.3.6.2](#) and [Section 5.3.6.3](#).

8.5 STATEMENT OF CONFIDENTIALITY AND PATIENT PRIVACY

The rights of the trial patient to privacy and protection of the data / patient notes obtained during the trial have to be ensured in accordance with local laws and regulations. Procedures for data handling and data protection need to be described in the patient information and informed consent form. Individual patient data obtained as a result of this trial is considered confidential and disclosure to third parties is prohibited with the exceptions noted below. Patient privacy will be ensured by using patient identification code numbers. Data protection and data security measures are implemented for the collection, storage and processing of patient data in accordance with the principles 6 and 12 of the WHO GCP handbook.

Treatment data may be given to the patient's personal physician or to other appropriate medical personnel responsible for the patient's welfare. Data generated as a result of the trial need to be available for inspection on request by the participating physicians, the sponsor's representatives, by the IRB / IEC and the regulatory authorities.

8.5.1 Collection, storage and future use of biological samples and corresponding data

Measures are in place to comply with the applicable rules for the collection, storage and future use of biological samples from clinical trial participants and the corresponding data, in particular

- * A Quality Management System has been implemented to ensure the adherence with the Principles of Good Clinical Practice as outlined in 'Note For Guidance On Good Clinical Practice' (CPMP/ICH/13 5/95)
- * The BI-internal facilities storing and analysing biological samples and data from clinical trial participants as well as the laboratories' activities for clinical trials sponsored by Boehringer Ingelheim are regularly audited. The analytical groups and the banking facility are therefore assessed to be qualified for the storage and use of biological samples and data collected in clinical trials.
- * Samples and data are used only if an appropriate informed consent is available.

8.6 TRIAL MILESTONES

The **start of the trial** is defined as the date of the enrolment (screening) of the first patient in the whole trial.

The **end of the trial** is defined as the date when the last patient in the whole trial completes the trial as per definition of trial completion in [Section 6.2.3.3](#).

The “**last-patient-last-visit-primary-endpoint-dose-finding**” is defined as the date when all patients in a respective dose finding cohort have completed at least the first treatment course. Thus, this milestone is defined for each dose finding cohorts (A, B, C and D (dose finding)).

The “**last-patient-last-visit-primary-endpoint-expansion**” (**Cohorts E and F**) is defined as the date when all patients in a respective expansion cohort have completed at least two tumour assessment time points or have permanently discontinued treatment or have completed the trial according to [Section 6.2.3](#). Thus, this milestone is defined for each expansion cohorts (E and F).

The “**last-patient-last-visit-primary-endpoint-expansion**” (**Cohorts D1 and D2**) is defined as the date when all patients have completed 18 months PFS observation or have permanently discontinued treatment or have completed the trial according to [Section 6.2.3](#). Thus, this milestone is defined for Cohorts D1 and D2.

The “**Last Patient Drug Discontinuation**” (LPDD) date is defined as the date on which the last patient at an individual trial site ends trial medication (as scheduled per protocol or prematurely). Individual Investigators will be notified of SUSARs occurring with the trial medication until 30 days after LPDD at their site. **Early termination of the trial** is defined as the premature termination of the trial due to any reason before the end of the trial as specified in this protocol.

Temporary halt of the trial is defined as any unplanned interruption of the trial by the sponsor with the intention to resume it.

Suspension of the trial is defined as an interruption of the trial based on a Health Authority request.

The IEC / competent authority in each participating EU member state will be notified about the trial milestones according to the respective laws.

A final report of the clinical trial data will be written only after all patients have completed the trial in all countries (EU or non-EU) to incorporate and consider all data in the report.

The sponsor will submit to the EU database a summary of the final trial results within one year from the end of a clinical trial as a whole, regardless of the country of the last patient (EU or non-EU).

For Japan only: when the trial is completed, the Investigator should inform the head of the trial site of the completion in writing, and the head of the trial site should promptly inform the IRB and sponsor of the completion in writing.

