 - age $<$ 60 years and amenorrheic (in the absence of tamoxifen, toremifene, ovarian suppression, or chemotherapy) for at least 12 months; and follicle-stimulating hormone (FSH) and estradiol within the postmenopausal range as per institutional reference ranges.
 - Postmenopausal status due to radiation-induced ovarian suppression must be confirmed by FSH and estradiol level in the postmenopausal range.
6. Histologically or cytologically proven diagnosis of breast cancer with evidence of locally advanced disease not amenable to curative resection or metastatic disease
7. HR+ (local lab results at screening or, if not available, at the time of diagnosis)
To fulfil the requirement of HR+ disease, the primary tumour or metastatic lesion of the breast cancer must express at least one of the hormone receptors (estrogen receptor [ER] or progesterone receptor [PgR]) by immunohistochemistry (IHC). Estrogen receptor and PgR assays are considered positive if there are at least 1% positive tumour nuclei in the sample as defined in the relevant American Society of Clinical Oncology (ASCO)/College of American Pathologists (CAP) Guidelines (Hammond et al. 2010).
8. HER2 negative (local lab results at screening or, if not available, at the time of diagnosis) as defined by the most recent American Society of Clinical Oncology (ASCO)/College of American Pathologists (CAP) Guidelines (Hammond et al. 2010).
9. Have a negative serum pregnancy test at baseline (within 14 days prior to randomization) and agree to use medically approved precautions to prevent pregnancy during the study and for 3 weeks following the last dose of abemaciclib and for at least 6 months after last dose of xentuzumab if postmenopausal status is due to ovarian suppression with a GnRH agonist.
10. Have either measurable disease or non-measurable bone only disease. Measurable and nonmeasurable diseases are defined according to the Response Evaluation Criteria in Solid Tumors (RECIST Version 1.1 [v1.1]. Nonmeasurable bone only disease may include any of the following: blastic bone lesions, lytic bone lesions without a measurable soft tissue component, or mixed lytic-blastic bone lesions without a measurable soft tissue component.

Cohort D1 and D2 only:

11. Patients must fulfil 1 of the following criteria:
 - a. Relapsed with radiologic evidence of progression while receiving neoadjuvant or adjuvant endocrine therapy, with no subsequent endocrine therapy received following progression.

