The primary endpoint for expansion part is disease control (DC) defined as best overall response of complete response (CR) or partial response (PR) or confirmed stable disease (SD) (lasting for at least 24 weeks) or Non-CR/ Non-PD (lasting for at least 24 weeks) where best

overall response is defined according to RECIST version 1.1 from first treatment administration until the earliest of disease progression, death or last evaluable tumour assessment before start of subsequent anti-cancer therapy.

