7.3.1 Primary endpoint analyses

For dose finding cohorts A, B, C, and D (dose finding):

In order to identify the MTD, the number of patients with DLTs during the MTD evaluation period at each dose level will be presented. Patients who discontinue during the first treatment course for reasons other than DLT will be excluded from the determination of MTD.

For expansion cohort E:

Objective response will be analysed in terms of objective response rate, defined as the proportion of patients with best overall response of CR or PR (note that no confirmation is required for best overall response).

For cohorts D1 and D2:

PFS rate at 18th month will be derived using Kaplan Meier method. Cohort D1 for visceral vs. cohort D2 for non-visceral will be displayed separately. The details will be described in the TSAP.

For expansion cohort F

DC will be analysed in terms of DC rate, defined as the proportion of patients with best overall response of CR, PR, SD lasting for at least 24 weeks or non-CR/non-PD lasting for at least 24 weeks.

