5.1.2 Cohort E

The primary endpoint for the expansion part cohort E is objective response (OR).

Objective response (OR)

OR is defined as best overall response of complete response (CR) or partial response (PR), where best overall response is determined according to Response Evaluation Criteria In Solid Tumours (RECIST) version 1.1 from date of first treatment administration until the earliest of disease progression, death or last evaluable tumour assessment before start of subsequent anti-cancer therapy.

Best overall response

An adequate RECIST tumour assessment includes an assessment of target lesions (only for patients with measurable disease at baseline), as well as radiological tests to evaluate non-target lesions if any and to search for new lesions. In case no RECIST tumour evaluation has been performed, the assessment will be set to missing.

Best overall response is calculated based on the “overall” visit response from each assessment. Best overall response represents the best response a patient has had during his/her time in the study until progression, last evaluable assessment in the absence of progression or the start of subsequent anti-cancer therapy. For patients whose progression event is death, best overall response will be calculated based on data until the last evaluable RECIST assessment prior to death. (note that no confirmation is required for best overall response)

The following categories of best overall response will be derived:

- Complete response (CR)
- Partial response (PR) – possible only for patients with measurable disease at baseline
- Stable disease (SD) – possible only for patients with measurable disease at baseline

Proprietary confidential information © 2021 Boehringer Ingelheim International GmbH or one or more of its affiliated companies

- Subcategory “SD \geq Week 24” for breast cancer and “SD \geq 6 weeks” for NSCLC: calculated from randomization/treatment start until the earliest of disease progression, death or last evaluable tumour assessment before start of subsequent anti-cancer therapy. Here SD \geq Week 24 includes SD \geq 161 days taking into account allowable CTP window.
- Non-CR/Non-PD – possible only for patients with non-measurable disease at baseline

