5.1.4 Cohort F

The primary endpoint for the expansion part cohort F is disease control (DC).

Disease control (DC)

DC is defined as best overall response of complete response (CR) or partial response (PR) or confirmed stable disease (SD) (i.e. lasting till at least Week 24, 161 days taking into account allowable CTP window) where best overall response is defined according to RECIST version 1.1 from first treatment administration until the earliest of disease progression, death or last evaluable tumour assessment before start of subsequent anti-cancer therapy.

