7.4.4 Cohort F

Disease control (DC)

DC as assessed by investigators is defined as a best overall response of CR or PR or SD and will be analysed. Descriptive statistics including number of treated patients, number of patients with objective response as best overall response and the corresponding percentages will be presented and evaluated.

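### The SAP's cohort F disease-control endpoint leaves out durable Non-CR/Non-PD and does not match Protocol 5.1.1 and 7.3.1

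*Protocol*

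**What the plan says.** **Protocol definition.** Section 7.3.1 defines the cohort F disease control (DC) rate as the proportion of patients with CR, PR, "SD lasting for at least 24 weeks or non-CR/non-PD lasting for at least 24 weeks". Section 5.1.1 lists the same components.

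**Eligibility.** Inclusion criterion 10 for cohorts D1, D2 and F (Protocol 3.3.2) reads: "Have either measurable disease or non-measurable bone only disease". In the SAP's list of best overall response categories (5.1.2), PR and SD are each marked "possible only for patients with measurable disease at baseline".

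**SAP definition.** SAP 5.1.4 counts CR, PR or confirmed SD, with the SD "lasting till at least Week 24, 161 days taking into account allowable CTP window". Non-CR/Non-PD is absent. SAP 7.4.4 says: "DC as assessed by investigators is defined as a best overall response of CR or PR or SD and will be analysed". It then reports the "number of patients with objective response as best overall response and the corresponding percentages". SAP 4.2 declares no changes from the protocol.

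**Elsewhere in the SAP.** Section 5.1.2 derives a category of Non-CR/Non-PD to at least Week 24 for breast cancer. Section 5.2.2.2 gives a complete breast-cancer DC definition that includes it, but the heading limits that text to cohorts E, D1 and D2.

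**Elsewhere in the protocol.** The synopsis gives cohort F disease control as CR, PR or SD of at least 24 weeks, without Non-CR/Non-PD. Section 3.2 still names the objective response rate as the primary endpoint for cohorts E and F.

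**Milestone.** Protocol 8.6 gives cohorts E and F one shared primary-endpoint milestone, reached once "all patients in a respective expansion cohort have completed at least two tumour assessment time points or have permanently discontinued treatment". Trial completion by a patient also satisfies it.

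**The concern.** The primary rate for cohort F depends on which paragraph is programmed. A bone-only patient can score only CR or Non-CR/Non-PD while free of progression. Under SAP 5.1.4 that patient is a failure unless CR is reached, however long the disease stays controlled. Under SAP 7.4.4 taken alone, SD of any length counts as success. Under the tabulation sentence of 7.4.4, the reported figure would be a different endpoint altogether. The errors run in opposite directions, so they cannot be relied on to cancel.

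The milestone raises a smaller, separate question of data maturity. An endpoint that needs 24 weeks is paired with a milestone that names no observation time, whereas the D1 and D2 milestone in the same section names their 18-month horizon. At a cut before day 161, patients with ongoing SD or Non-CR/Non-PD could not yet be classified. Scoring them as failures would lower the rate. Patients already in CR or PR would be unaffected.

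**Working it through.** **1. Definitions side by side**

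| Source | CR, PR | SD | Non-CR/Non-PD |
|---|---|---|---|
| Protocol 5.1.1, 7.3.1 | yes | at least 24 weeks | at least 24 weeks |
| Protocol synopsis | yes | at least 24 weeks | not listed |
| Protocol 3.2 | objective response only | no | no |
| SAP 5.1.4 | yes | at least 161 days | not listed |
| SAP 7.4.4, definition | yes | no minimum | not listed |
| SAP 7.4.4, tabulation | objective response only | no | no |
| SAP 5.2.2.2, breast cancer (E, D1, D2 heading) | yes | at least 161 days | at least 161 days |

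The 161 days is explained in SAP 5.1.2 as the allowed Week 24 window. It is a minor operational choice and not part of the problem.

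**2. The plan's own figures.** Protocol 7.7 takes n = 20. It states a probability of 87% of at least 10 events at a true DC rate of 60%, and 3% of at least 8 events at 20%. Exact binomial tails give P(X ≥ 10 | 20, 0.60) = 0.872 and P(X ≥ 8 | 20, 0.20) = 0.032. Both reproduce.

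**3. Effect of SAP 5.1.4.** The documents do not give the number of bone-only patients, so assume b of 20. Assume also that all their disease control is Non-CR/Non-PD, so that every one is scored as a failure. The expected rate is (20 − b) × 0.60 / 20, and the event count is Binomial(20 − b, 0.60).

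| b | Expected rate | P(at least 10) |
|---|---|---|
| 0 | 60% | 0.87 |
| 2 | 10.8/20 = 54% | 0.74 |
| 4 | 9.6/20 = 48% | 0.53 |
| 6 | 8.4/20 = 42% | 0.28 |

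Treating bone-only status as a random share of 10%, 20% or 30% gives 0.72, 0.52 and 0.31, which leads to the same conclusion.

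**4. Effect of SAP 7.4.4 if read without 5.1.4.** Suppose true 24-week DC is 20% and a further 5 or 10 percentage points of patients have only shorter SD (assumed). The apparent rate is then 25% or 30%. P(X ≥ 8 | 20, 0.25) = 0.10 and P(X ≥ 8 | 20, 0.30) = 0.23, against 0.03.

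**5. Milestone timing.** SAP 6.7.2 sets the due day as 7 × week + 1.

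- Second 8-weekly scan: 16 × 7 + 1 = day 113, and 161 − 113 = 48 days short.
- With the 105 to 119 day window printed in the flow charts of other cohorts: 161 − 119 = 42 to 161 − 105 = 56 days short.
- Second 12-weekly scan: 24 × 7 + 1 = day 169, so no gap.
- Discontinuation route: no minimum time, hence no fixed gap.

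The cohort F flow chart leaves imaging to institutional practice, so any of these can apply.

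**6. Effect of an early cut.** Suppose m patients are under 161 days at the cut, and half of true DC (30 points, assumed) is CR or PR and counts at once. The count is Binomial(20 − m, 0.60) + Binomial(m, 0.30). For m = 1 the expected rate is 58.5% and P(at least 10) is 0.84. For m = 4 they are 54% and 0.73.

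**The case against.** **On the definition.** The SAP says it is based on the protocol's analysis specification, and it declares no changes. Its section 5.1.2 already derives the missing breast-cancer category and explains the 161-day cut-off for SD and Non-CR/Non-PD together. The heading in 5.2.2.2 may be limited to E, D1 and D2 only because disease control is secondary there. The objective-response sentence in 7.4.4 repeats the wording of 7.4.2 for cohort E and looks carried over. The missing SD duration is supplied in 5.1.4. All this is fair. It supports a drafting omission, and a reader who inferred a deliberate change of endpoint would go beyond the documents. It does not remove the defect. Section 5.1.4 is the place that defines the cohort F primary endpoint, and as written it excludes these patients. Section 7.5.2.2 uses a similar short form for the secondary endpoint but points back to 5.2.2.2, whereas 7.4.4 has no such pointer.

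Nor is the SAP alone at odds. The protocol synopsis agrees with SAP 5.1.4 on components, and section 3.2 names another endpoint. That is a reason to reconcile all the texts.

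**On the milestone.** A reader might infer that cohort F will be analysed at about week 16. The documents do not support that:

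- Protocol 7.3 ties the dose-finding analysis to its milestone but makes no such link for the expansion cohorts, leaving details to the SAP.
- Protocol 8.6 holds the final report until all patients have completed the trial.
- Cohort F patients without progression stay in tumour follow-up after treatment stops.
- The milestone requires every patient to qualify, so only the latest enrolled could be immature.
- Protocol 3.3.4.2 ends xentuzumab by May 2023, subject to at least two years on it for patients who tolerate it without progression. This implies, by inference only, starts by about May 2021, well over 161 days before the revision of 04 Mar 2022.

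What remains is narrow. Protocol 7.3 and 7.4 permit analysis before study end, and SAP Table 6.6: 1 foresees patients still on treatment at a snapshot. The SAP history table mentions an interim report, without naming cohort F. The SAP text available, which is redacted in places, gives no cohort F cut-off.

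**Conclusion.** The definition mismatch stands as the main point. SAP 5.1.4 and 7.4.4 do not implement the cohort F primary endpoint of Protocol 5.1.1 and 7.3.1, and the protocol's own synopsis and section 3.2 disagree with those sections. As SAP 5.1.4 is written, each bone-only patient with durable control short of CR moves from success to failure, whatever the date of the cut.

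The size depends on the number of such patients, which the documents do not give. With 2 to 6 of 20, the expected rate drops by 6 to 18 points from 60%. The short-SD effect of 7.4.4 arises only if 5.1.4 is ignored. The trial is descriptive, so the probabilities are operating figures of the kind shown in Protocol 7.7 and not test errors. It does not follow that the reported rate will be wrong, since a programmer who follows Protocol 7.3.1 would get it right.

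The milestone mismatch is real but secondary. It depends on the scan interval and on someone choosing that date for a cut, and it may be moot for patients ongoing at the current revision.

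**What to change.** 1. In SAP 5.1.4 and 7.4.4, define cohort F disease control as CR, PR, or SD or Non-CR/Non-PD lasting at least 24 weeks (at least 161 days), and tabulate the number and percentage of patients with disease control. The derivation in SAP 5.1.2 already supplies the category.
2. Bring the protocol synopsis and Protocol 3.2 into line with Protocol 5.1.1 and 7.3.1.
3. For any cohort F data cut, state in the SAP that each patient needs either an evaluable assessment on or after day 161 or a disease-control status already settled (CR or PR, progression, death, new anti-cancer therapy, withdrawal or loss to follow-up). Stopping treatment alone should not suffice. At an earlier look, report ongoing SD or Non-CR/Non-PD under 161 days as not yet evaluable. If Protocol 8.6 is reopened, give cohort F its own milestone in these terms and leave the two-assessment rule for cohort E.

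The cost is wording, with no extra patients or scans. A snapshot tied to the current milestone might move later. By the scan route on the 8-weekly windows this is 42 to 56 days, or 6 to 8 weeks. By the discontinuation route there is no fixed figure.
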